## 1 List of Abbreviations

Table 1-1. List of abbreviations

Abbreviation	Description
ADL	Activities of Daily Living
ADR	Adverse Drug Reaction
AE	Adverse Event
CRF	Case Report Form
CTCAE	Common Terminology Criteria for Adverse Events
GCP	Good Clinical Practice
HA	Hyaluronic Acid
ICH	International Council for Harmonization of Technical Requirements for Pharmaceuticals
MedDRA	Medical Dictionary for Regulatory Activities
NLF	Nasolabial Fold
NSAID	Non-Steroidal Anti-Inflammatory Drug
OTC	Over-the-Counter
PGAIS	Physician Global Aesthetic Improvement Scale
PMS	Postmarketing Surveillance
PT	Preferred Term
SOC	System Organ Class
SOP	Standard Operating Procedure
WHO	World Health Organization
WSRS	Wrinkle Severity Rating Scale

## 4 Abstract

### Title

A randomized, double-masked, active-controlled, within-subject equivalency clinical trial to compare effectiveness and safety of Lunaphil Ultra (Hyaluronic acid, produced by Espad Pharmed Co.) versus Juvederm Ultra 4® (Hyaluronic acid, produced by Allergan Co.) for the management of moderate or severe nasolabial folds (NLFs)

[name]

Department of Dermatology, Razi Hospital, Tehran University of Medical Sciences, Tehran, Iran

### Keywords

Lunaphil Ultra, Hyaluronic Acid, Nasolabial Folds

### Rationale and Background

Skin aging is a complex process that results in various changes in the skin, including wrinkles, sun spots, and sagging skin. The NLF is a natural change that becomes more prominent with aging and significantly affects the beauty of the

facial skin. Dermal fillers, particularly HA fillers, are commonly used to correct these signs of aging. This study aims to compare the effectiveness and safety of Lunaphil Ultra with Juvederm Ultra 4® for treating NLFs.

### **Research Question and Objectives**

Primary objective:

Effectiveness assessment of Lunaphil Ultra

Secondary objectives:

Effectiveness and safety assessment of Lunaphil Ultra

### **Study Design**

This is a randomized, double-masked, active controlled, within-subject, and equivalency clinical trial.

### **Setting**

Subjects will be treated with Lunaphil Ultra in one NLF and Juvederm Ultra 4® in the opposite NLF.

A total of 108 participants will be enrolled in the study. For each participant, the products will be injected in the first visit and if needed an additional injection will be done (touch-up) at visit 2 (week 2). The duration of the study is 24 weeks for each participant.

### **Subjects and study size, including drop-outs**

A population of 108 participants will be enrolled in the study, and during 24 weeks, study-related data will be collected.

### **Variables and Data Sources**

Lunaphil Ultra will be administered over a 2-week period (initial treatment plus one touch-up) to achieve optimal correction of the NLFs.

The primary objective of this study is effectiveness assessment, including the mean level of improvement from baseline in NLF severity score by Wrinkle Severity Rating Scale (WSRS) at week 24.

Variables in this study includes patient demographic information (age, sex), history of filler injection, baseline WSRS and subsequent scores at other visits, patient's medical history, patient's medications, injection volume, receipt of touch-up treatment, Physician Global Aesthetic Improvement Scale (PGAIS) at each visit, and adverse events (AE) reporting.

### **Data Analysis**

The primary endpoint will be assessed by measuring the mean level of improvement from baseline in NLFs severity score using either a paired t-test or a signed-rank test.

The number of patients with an improved score for the PGAIS, proportion of NLFs with clinically significant improvement and the number of NLFs receiving touch-up treatment will be analyzed using a McNemar test. Injection volume to obtain optimal result will be analyzed with a paired t-test or a signed-rank test.

The safety data will be analyzed primarily using incidence and frequency. AEs' severity, seriousness, and causality assessment will be reported.

## 5 Rationale and Background

Skin aging is a complex and multifactorial process resulting in various functional and aesthetic changes in the skin (1). It is an inevitable process that can be described clinically as features of wrinkles, sun spots, uneven skin color, and sagging skin (2). Additional clinical findings include tear trough, a drop of the angle of the mouth, loss of definition in the mandibular border, platysmal bands, evident veins, and NLFs as one of the typical clinical manifestations of facial aging (3).

The perception of health and age is a critical aspect in the common judgment of attractiveness and people are judged to be less attractive as they age (4). Attractiveness influences both self-perception and social behavior and is related to traits such as self-confidence and social acceptance. Therefore, aesthetic interventions can improve psychological well-being and quality of life (5).

Dermal fillers are widely used for the correction of deep wrinkles, including NLFs. Treatments with dermal fillers provide favorable aesthetic outcomes with minimal invasiveness and no downtime following surgical procedures (6). Hyaluronic acid (HA) fillers, the most popular dermal fillers (7), demonstrate desirable effects on the fibroblast phenotype, including higher cell proliferation and type I collagen synthesis (8). HA fillers have predictable efficacy, a good safety profile, quick recovery, and simplicity in administration (9, 10).

Different factors, including HA concentration, polymer chain length, and crosslinking degree or technology, influence filler properties such as the requisite needle size, particle size, duration, extrusion force, and elastic Modulus (G'). All of these factors will critically influence product selection and indication (11). Among these factors, crosslinking is essential to slowing down the enzymatic degradation rate of the HA by endogenous hyaluronidase and prolonging the product's half-life. The extent of crosslinking strongly impacts the biophysical and biological properties of a filler, including tissue integration, water uptake, resistance to degradation, and filler biocompatibility and consequently might have clinical implications (12).

Lunaphil Ultra intradermal filler is a cross-linked HA soft tissue filler manufactured by Espad Pharmed Company. It contains 24 mg/ml of HA and 0.3% lidocaine as a supplemental anesthetic. Since pain is the most commonly reported complaint with dermal fillers, a local anesthetic like lidocaine is included in their formulation to reduce procedural pain and bypass the need for additional anesthesia (13).

The aim of this study is to compare the effectiveness and safety of Lunaphil Ultra (Hyaluronic acid, produced by Espad Pharmed Co.) versus Juvederm Ultra 4® (Hyaluronic acid, produced by Allergan Co.) in managing moderate or severe NLFs.

## 6 Research Question and Objectives

Primary objective:

- Mean level of improvement from baseline in NLF severity score by WSRS at week 24

Secondary objective:

- Number of subjects with an improvement score based on PGAIS at week 24
- Proportion of NLFs maintaining a clinically significant improvement in NLF severity score ( $\geq 1$ -point reduction from baseline) at week 24

- The injected volume to obtain optimal aesthetic result (initial treatment + touch-up)
- The number of NLFs receiving touch-up treatment
- The incidence, severity and causal relationship of adverse events

## 7 Amendments and Updates

There are no amendments and updates throughout the study.

## 8 Research Methods

### 8.1 Study Design

This is a randomized, double-masked, active controlled, within-subject, and equivalency study to compare the effectiveness and safety of Lunaphil Ultra (Hyaluronic acid, produced by Espad Pharmed Co.) versus Juvederm Ultra 4® (Hyaluronic acid, produced by Allergan Co.) for the management of moderate or severe NLFs.

### 8.2 Setting

#### 8.2.1 *Subjects*

A total of 108 participants with moderate to severe NLFs will be enrolled in the study.

#### **Inclusion Criteria**

- Subjects  $\geq$  30 years of age
- Visible bilateral NLFs that are approximately symmetrical and have an equal severity ranging from moderate to severe (assessed at the deepest part)
- Able to follow study instructions and likely to complete all required visits
- Signed informed consent

#### **Exclusion Criteria**

- History of bleeding disorders or participants receiving or recently exposed ( $\leq$  3 weeks) to continuous treatment with thrombolytics, anticoagulants, platelet inhibitors, or NSAIDs
- Acute herpetic eruption
- Known susceptibility to keloid formation, hypertrophic scarring or clinically significant skin pigmentation disorders
- Known sensitivity to local anesthetics of the amide type (such as lidocaine), history of hypersensitivity to gram-positive bacterial proteins, history of multiple severe allergies, history of anaphylactic shock
- Known hypersensitivity to any component of the study products or excipients (like hyaluronic acid)
- History of receiving immune therapy or a history of autoimmune disease
- History of active chronic debilitating systemic disease

- History of connective tissue disease, history of malignancy (except for non-melanoma skin cancer) within the last 5 years
- Clinically significant active dermatologic disorders within the last 6 months
- Use of oral retinoids, OTC or prescription antiwrinkle treatments, microdermabrasion, or chemical peels in the NLF area within the last 4 weeks or intention to use them during the study
- Any prior cosmetic procedure or tissue augmentation at the NLF injection site within 1 year before study entry (or intent to undergo such a procedure during the study)
- Pregnancy or breastfeeding

#### **Withdrawal Criteria**

- Withdrawal of consent by the participant
- Noncompliance, including refusal of study medical requirements, refusal of procedures as stated in the study protocol, or use of prohibited medications
- The occurrence of an undesirable event that causes the investigator to consider the participant's exclusion from the study
- Not possible to follow the participant's condition (Loss to follow-up)
- Change in participant's conditions, which needs change of treatment due to investigator decision or administration of prohibited medications in the protocol

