### 8.3 Study Timeline

Time point	Study period						Visit 4 24 weeks ± 3 days
	Screening	Intervention					
Time	Screening visit	Visit 1	Visit 2, * (Touch-up)	Visit 2, 2 weeks ± 3 days	Visit 3 4 weeks ± 3 days		
Informed consent	×						
Eligibility Criteria	×						
Randomization and allocation		×					
Medical History	×						
Face photography	×	×		×	×	×	×
Intervention		×		×			
NLF severity score assessment	×			×	×	×	×
PGAIS assessment		***		×	×	×	×
Concomitant Medications	×	×		×	×	×	×
Adverse Events reporting	×	×		×	×	×	×

\* Two treatments will be allowed over a 2-week period (initial treatment plus one touch-up) to achieve optimal correction of the NLFs. The level of correction will be assessed by the evaluating investigator at week 2 after the initial treatment and, if less than optimal, the treating investigator will be directed to retreat the under corrected NLF(s).

\*\* This visit is only conducted in patients with touch-up injection.

\*\*\* PGAIS in visit 1 is assessed after the intervention.

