4. Not possible to follow the participant's condition (Loss to follow-up)

5. Change in participant's conditions, which needs change of treatment due to investigator decision or administration of prohibited medications in the protocol

Data sources and measurement

All data will be collected by specialists and recorded in a booklet comprising five visits. Baseline information (demographics, past medical history, history of filler injection, patients' medications), intervention information (e.g., dosage at visit 1 and touch up), WSRS, and PGAIS will be recorded.

All adverse events (AEs) will be documented and categorized according to their frequency, severity (graded using the Common Terminology Criteria for Adverse Events version 5.0) (14), and their assessed causality, following the World Health Organization guidelines (15). The AEs will be reported using the Medical Dictionary for Regulatory Activities (MedDRA) under both the preferred term (PT) and system organ class (SOC) (16). Serious adverse events (SAEs) will be documented in compliance with the E2B(R2) guideline (17) and will be defined as any AE that “results in death, is life-threatening, requires inpatient hospitalization or prolongation of existing hospitalization, results in persistent or significant disability/incapacity, is a congenital anomaly/birth defect, or other medically important condition.”

Section 4: General issues for statistical analysis

Analysis populations

Primary efficacy will be analyzed on a per-protocol population. Also, the primary outcome and secondary key variables of the study will be examined on the intention-to-treat population, and sensitivity analysis will be used to compare the primary outcome in the two populations. All analyzes of complications will be performed based on the safety population.

1. Per-protocol population: all patients who were randomly treated with the study drug and did not have a major deviation from the protocol.
2. Intention-to-treat population: all patients randomly assigned to one of the treatment groups. Patients are analyzed according to the treatment they received randomly.
3. Safety population: All patients who randomly received at least one dose of the study drug. Patients are analyzed according to the treatment they actually received.

Protocol violations and deviations

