A protocol deviation refers to any change, non-compliance, or departure from the approved protocol such as enrolling a participant who did not meet all the inclusion/exclusion criteria, visit non-compliance, incorrect execution of the consent form, participant declines to complete scheduled research activities, use of unapproved recruitment procedures, use of an unapproved version of the Participant Information and Consent Form, dispensing or dosing error for study medication/drug, and any change, divergence, or departure from the study design or procedures defined in the protocol. The per-protocol (PP) population is a subset of the Intention-To-Treat (ITT) population, which includes participants who completed the study without any major violations of the protocol. Description of which protocol deviations will be summarized. No participants will be excluded from the ITT analyses due to protocol deviations.

Statistical Software

The analysis will be carried out using Stata (StataCorp LP, USA) and R statistical software.

Missing Data

The missing WSRS scores at week 24 for participants with available week 12 data will be imputed based on their WSRS scores at week 12. For participants with missing WSRS scores at week 12, no imputation will be performed. In the ITT population, imputation for this outcome will be conducted as described above.

Outlier data

Outliers are identified by examining standard charts, and those that are visually "distinct" are evaluated to check the impact on the results by comparing the results of the analysis with and without outliers.

Data Transformations

No transformations of raw data are planned prior to statistical analysis. All variables will be analyzed using their original measurement scales, unless transformation is deemed necessary during model diagnostics. In such cases, justification and details will be documented in the statistical outputs and Clinical Study Report (CSR).

Multiple comparisons and multiplicity

No formal procedures for multiplicity adjustment are planned for this study, as the study was not designed to perform multiple statistical comparisons for primary or key secondary endpoints. Therefore, the overall Type I error rate will not be adjusted.

Covariate Adjustment

No covariate adjustment will be done.

Planned subgroup analysis

No subgroup analysis will be done.

Section 5: Outcome Variables

Primary Outcomes

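### Withdrawal for non-compliance or prohibited medication, with no assessments planned afterwards, weakens the ITT check on the primary per-protocol analysis

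*Protocol*

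**What the plan says.** **Withdrawal.** The Withdrawal Criteria in protocol section 8.2.1 include "Noncompliance, including refusal of study medical requirements, refusal of procedures as stated in the study protocol, or use of prohibited medications". The last item of the list returns to the subject, covering a change in condition that "needs change of treatment due to investigator decision or administration of prohibited medications in the protocol". Another item, on undesirable events, speaks of "exclusion from the study". The SAP gives the same criteria in its synopsis and in Section 3. Neither document separates stopping treatment from stopping follow-up, and neither describes any assessment after withdrawal.

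**Timing.** Product is injected at visit 1 and, if needed, once more at the week-2 touch-up (protocol 8.3). The protocol abstract, under Setting, states: "The duration of the study is 24 weeks for each participant". The primary endpoint is WSRS improvement at week 24.

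**Analysis sets (SAP Section 4).** "Primary efficacy will be analyzed on a per-protocol population". ITT comprises everyone randomized, and a comparison of the two sets is the planned sensitivity analysis. On deviations the SAP says: "No participants will be excluded from the ITT analyses due to protocol deviations". The same paragraph limits PP to those who finished the study without a major violation.

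**Missing data (SAP Section 4).** A missing week-24 WSRS is imputed from the week-12 score where there is one. Otherwise: "For participants with missing WSRS scores at week 12, no imputation will be performed".

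**The concern.** The ITT analysis is there to show whether leaving out deviators changes the equivalence conclusion. For that it needs deviators' week-24 scores. The withdrawal criteria cover much of the same behaviour that the SAP lists as deviations: declining scheduled study activities, for example, is a deviation in the SAP and also matches the refusal-of-procedures trigger. After the touch-up there is no further study treatment to stop, so a later withdrawal can only remove outcome data.

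If withdrawn deviators are not assessed again, the people whom ITT should add back to PP are either absent from both analyses or represented by a score taken 12 weeks before the endpoint. Agreement between PP and ITT would then give weaker reassurance than the SAP intends, and selective loss could go unnoticed. This matters more than usual because PP is primary and ITT is the only planned check on it.

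**Working it through.** **Inputs.** From protocol 8.6 and the SAP Sample size section: 97 evaluable pairs, SD of paired differences 0.51, limits ±0.17, true difference 0, 2.5% per one-sided test, 10% drop-out, 108 enrolled. From SAP Section 7: equivalence requires the whole 95% CI to lie inside ±0.17. The week-12 visit is taken from the SAP timeline. The documents do not give the number withdrawn for non-compliance, when they leave, or their paired differences. These are assumed below.

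**1. Reproduce the plan's figures.**
- Normal approximation: ((1.960 + 1.282) × 0.51 / 0.17)² = 94.6, so 95.
- Exact paired-t TOST power: 79.7% at n = 96 and 80.3% at n = 97, so 97 is the smallest n that reaches 80%.
- 97 / 0.9 = 107.8, so 108.

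The plan's figures reproduce.

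**2. What happens to each kind of deviator.**

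| Participant | Week-24 score used in ITT | In PP |
|---|---|---|
| Withdrawn before week 12 | None, not imputed | No |
| Withdrawn after week 12 | Week-12 score carried forward | No (not a completer) |
| Major deviation, not withdrawn | Observed | No |

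**3. How far ITT and PP separate.** Assume that 11 of 108 are withdrawn (108 − 97, the whole drop-out allowance) and that there are no other major deviators.

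| Timing of the 11 withdrawals | ITT n with a score | PP n | In neither |
|---|---|---|---|
| All before week 12 | 97 (all observed) | 97 | 11 |
| 5 before, 6 after | 103 (97 observed + 6 carried forward) | 97 | 5 |
| All after week 12 | 108 (97 observed + 11 carried forward) | 97 | 0 |

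If 3 further participants have a major deviation but are not withdrawn, PP falls to 94 and ITT exceeds it by 3, 9 or 14. The two sets coincide only when every major deviator leaves before week 12.

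**4. Power.** At n = 108 it is 85.9%, and at n = 97 it is 80.3%. Losing 11 pairs therefore lands on the design target.

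**5. Possible bias.** Shift between the all-randomized mean and the completer mean = (fraction withdrawn) × (departure of the withdrawn participants' mean paired difference from that of completers). With 10% withdrawn:
- departure 0.17 (equal to the margin): 0.10 × 0.17 = 0.017, which is 10% of the margin;
- departure 0.5: 0.10 × 0.5 = 0.05, and 0.05 / 0.17 = 29% of the margin.

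**6. Room under the decision rule, holding the SD at 0.51.**
- n = 97: half-width = t(0.975, 96) × 0.51 / √97 = 0.103, so the observed difference must lie within 0.17 − 0.103 = 0.067 of zero.
- n = 108: half-width 0.097, room 0.073.

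A shift of 0.05 is about 75% of 0.067, and a shift of 0.017 is about 25%. Neither reverses the result if the completers' difference is zero. With a shift of 0.05, completers whose mean difference lies between about 0.023 (0.073 − 0.05) and 0.067 in the same direction would pass, while the full set of 108 would not.

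**The case against.** The strongest reply is that the documents do not say what a critic might read into them. Four parts of it deserve an answer.

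- **A reader might infer that week-24 scores of withdrawn participants are never collected.** No sentence says so. The documents are silent on assessment after withdrawal. This stands: the supportable statement is that no such assessment is planned.
- **A reader might infer that the ITT rule and the withdrawal rule contradict each other, or that the PP-versus-ITT check is emptied.** The ITT sentence concerns membership of the set and does not promise observed scores, and the SAP foresees missing ones. Participants carried forward from week 12 are in ITT but not in PP. So are deviators who need not be withdrawn, such as those with an eligibility, consent-form or dosing error. This stands: the check is weakened, and it is empty only in the extreme case in step 3.
- **A reader might infer a loss of power.** The sample size already allows for 10% loss. This stands in full.
- **The bias example is severe.** A departure of 0.5 is about one SD (0.5 / 0.51) and 2.9 times the margin (0.5 / 0.17), in one direction for everyone withdrawn. Each withdrawal removes both sides of the face, so there is no differential drop-out between products. If only half of the withdrawals precede week 12, the wholly unseen part at 0.5 is 0.05 × 0.5 = 0.025, or 15% of the margin. This limits the size, and the example should be read as the upper part of a range.

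It is also fair that participants who refuse procedures may not come back for more of them. None of this answers the remaining point: scores that could be observed at visits already scheduled are not planned for, and imputation does not recover them.

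**Conclusion.** The concern holds as a weakness of the planned check. As written, the plan provides no post-withdrawal assessment for people withdrawn for the kinds of deviation that ITT is meant to retain. ITT therefore moves towards PP plus week-12 carry-forward, and agreement between the two sets would be less informative than the SAP intends. The documents do not support calling the check empty, the data certainly lost or the trial underpowered.

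The size is uncertain. With 10% withdrawn, a shift of about 0.017 to 0.05 is possible against about 0.067 of room at n = 97. That range rests on an assumed withdrawal fraction (the all-cause drop-out allowance, not a non-compliance rate) and an assumed departure of 0.17 to 0.5 points. It also requires withdrawal to be related to the side-to-side difference. If it is unrelated, the expected shift is zero. The change is worth making because it is cheap and bears on the only check of the primary analysis.

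**What to change.** In the Withdrawal Criteria of both documents, leave the clinical withdrawal decision as it is and separate it from data collection:

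- Unless the participant withdraws consent or contact is lost, seek the already scheduled WSRS, PGAIS and adverse-event assessments through week 24.
- In SAP Section 4, use these observed scores in ITT, so that the week-12 rule applies only when the week-24 score could not be obtained.
- Exclude from PP those whose deviation is classed as major, and state which deviations count as major, since the SAP does not define the term.
- Report how many were withdrawn for each reason, before and after week 12, and how many ITT scores are observed, carried forward or absent.

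The cost is a few sentences in each document and a small number of follow-up visits. Some participants, especially those withdrawn for refusing procedures, will not return, so the gain is partial. Full recovery of the 11 assumed withdrawals, from 97 to 108 observed pairs, is a ceiling.
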